1 LIST OF ABBREVIATIONS AND ACRONYMS

AE	Adverse Experience
EAE	Expedited Adverse Experience
FSR	Final Study Report
RSC	Regulatory Support Center
SAE	Serious Adverse Event
SAP	Statistical Analysis Plan
SMB	Safety Monitoring Board

2 OVERVIEW

The following describes the Statistical Analysis Plan (SAP) for the analysis of safety data from HVTN 302 for Safety Monitoring Board (SMB) reports and the Final Study Report (FSR) for Safety.

3 PROTOCOL SUMMARY

Participants will receive BG505 MD39.3 mRNA, BG505 MD39.3 gp151 mRNA or BG505 MD39.3 gp151 CD4KO mRNA, at doses of 100 mcg or 250mcg, administered via intramuscular (IM) injections into the deltoid muscle. Participants will be evaluated for safety and immune responses through blood and lymph node fine-needle aspiration collection at specified timepoints throughout the study. The study schema is below:

Table 1-1 Schema

Study Arm	N	Dose (mcg)	Month 0	Month 2	Month 6
Part A					
Group 1	18	100	BG505 MD39.3 mRNA	BG505 MD39.3 mRNA	BG505 MD39.3 mRNA
Group 2	18	100	BG505 MD39.3 gp151 mRNA	BG505 MD39.3 gp151 mRNA	BG505 MD39.3 gp151 mRNA
Group 3	18	100	BG505 MD39.3 gp151 CD4KO mRNA	BG505 MD39.3 gp151 CD4KO mRNA	BG505 MD39.3 gp151 CD4KO mRNA
Part B					
Group 4	18	250	BG505 MD39.3 mRNA	BG505 MD39.3 mRNA	BG505 MD39.3 mRNA
Group 5	18	250	BG505 MD39.3 gp151 mRNA	BG505 MD39.3 gp151 mRNA	BG505 MD39.3 gp151 mRNA
Group 6	18	250	BG505 MD39.3 gp151 CD4KO mRNA	BG505 MD39.3 gp151 CD4KO mRNA	BG505 MD39.3 gp151 CD4KO mRNA
Total	108				

Study Design

This is a multicenter, randomized, open-label, Phase 1 study to evaluate the safety and immunogenicity of BG505 MD39.3, BG505 MD39.3 gp151, and BG505 MD39.3 gp151 CD4KO HIV trimer mRNA in healthy adults. The primary hypothesis is BG505 MD39.3 soluble and membrane-bound trimer mRNA vaccines will be safe and well-tolerated among HIV-uninfected individuals and will elicit autologous neutralizing antibodies.

Study Population

All inclusion and exclusion criteria must be met for eligibility. Screening procedures to determine eligibility must be performed within 56 days prior to enrollment.

Investigators should always use good clinical judgment in considering a volunteer's overall fitness for trial participation. Some volunteers may not be appropriate for enrollment even if they meet all inclusion/exclusion criteria. Medical, psychiatric, occupational, or other conditions may make evaluation of safety and/or immunogenicity difficult, and some volunteers may be poor candidates for retention.

Vaccine Regimen

Group 1

100 mcg of BG505 MD39.3 mRNA (labeled as mRNA-1574v1-GP140) to be administered as 0.5 mL doses intramuscularly (IM) at months 0, 2, and 6

Group 2

100 mcg of BG505 MD39.3 gp151 mRNA (labeled as mRNA-1574v2-GP151) to be administered as 0.5 mL doses intramuscularly (IM) at months 0, 2, and 6

Group 3

100 mcg of BG505 MD39.3 gp151 CD4KO mRNA (labeled as mRNA-1574v3-CD4KO-GP151) to be administered as 0.5 mL doses intramuscularly (IM) at months 0, 2, and 6

Group 4

250 mcg of BG505 MD39.3 mRNA (labeled as mRNA-1574v1-GP140) to be administered as 0.5 mL doses intramuscularly (IM) at months 0, 2, and 6

Group 5

250 mcg of BG505 MD39.3 gp151 mRNA (labeled as mRNA-1574v2-GP151) to be administered as 0.5 mL doses intramuscularly (IM) at months 0, 2, and 6

Group 6

250 mcg of BG505 MD39.3 gp151 CD4KO mRNA (labeled as mRNA-1574v3-CD4KO-GP151) to be administered as 0.5 mL doses intramuscularly (IM) at months 0, 2, and 6

4 SAFETY OBJECTIVES AND ENDPOINTS

Primary Objectives and Endpoints

Primary objective 1:

To evaluate the safety and tolerability of BG505 MD39.3 trimer mRNA vaccines in healthy, HIV-uninfected adults

Primary endpoint 1:

Local and systemic reactogenicity signs and symptoms for a minimum of seven days following receipt of any study product. Laboratory measures of safety. All adverse events (AEs) for thirty days after receipt of study vaccination

All serious adverse events (SAEs), medically attended adverse events (MAAEs), adverse events of special interest (AESIs), and AEs leading to early participant withdrawal or permanent discontinuation will be collected throughout the study

5 COHORT DEFINITION

Recruitment will target enrolling 108 healthy, HIV-uninfected adult participants from 18-55 years old.

Since enrollment is concurrent with receiving the first study vaccination, all participants will provide some safety data.

6 POTENTIAL CONFOUNDERS

Characterization of the safety of the vaccine is susceptible to confounding by adverse events not related to the vaccine that by chance occur more often in one arm of the trial than another. Therefore analyses involving adverse events will incorporate the reported relationship to product as assessed by HVTN staff.

7 RANDOMIZATION

Participants will first be randomized in a 1:1:1 ratio into the Part A sentinel safety cohort. If safety criteria are met, enrollment will proceed with Part B sentinel group of n=12 with 1:1:1 randomization and the remainder of Part A (n=42) with 1:1:1 randomization, with some sites enrolling into the Part B sentinel cohort while other sites are enrolling the remainder of Part A. Once the safety criteria for the Part B sentinel safety cohort have been met, the remaining Part B participants (n=42) will be enrolled with 1:1:1 randomization.

Randomization to Groups 1-3 will be stratified by willingness to consent to FNA and/or leukapheresis. A maximum of 27 participants in total that do NOT consent to either FNA and leukapheresis collection will be enrolled.

A participant's randomization assignment will be computer generated and provided to the HVTN CRS pharmacist through a web-based randomization system. At each institution, the pharmacist with primary responsibility for dispensing study products is charged with maintaining security of the treatment assignments (except in emergency situations as specified in the HVTN Manual of Operations [MOP]).

8 BLINDING

This study is open-label.

9 SAMPLE SIZE

Recruitment will target enrolling 108 healthy, HIV-uninfected adult participants.

108 healthy, HIV-uninfected adult participants will be enrolled into three 100 mcg vaccine dose groups in Part A and into three 250 mcg vaccine dose groups in Part B (n=18 per group). The study will begin by enrolling a Part A sentinel safety cohort with 1:1:1 randomization into Groups 1-3 (of n=12) to be evaluated for safety two weeks after the first vaccination. Participants that are randomized but not enrolled will be replaced to ensure that at least 12 participants are enrolled before initiation of the planned enrollment pause.

The PSRT will convene after the 12th participant in the Part A sentinel safety cohort has received their first vaccination and completed the 2 week post vaccination safety visit to determine if further participants should be enrolled. If safety criteria are met, enrollment will proceed with Part B sentinel group of n=12 with 1:1:1 randomization and the remainder of Part A (n=42) with 1:1:1 randomization. Once the safety criteria for the Part B sentinel safety cohort have been met, the remaining Part B participants (n=42) will be enrolled with 1:1:1 randomization. Figure 9-1 illustrates this plan.

Enrollment/Randomization plan

[figure not shown]

Figure 9-1 Schema of enrollment strategy

Since enrollment is concurrent with receiving the first study vaccination, all participants will provide some safety data. However, for immunogenicity analyses, it is possible that data may be missing for various reasons, such as participants terminating from the study early, problems in shipping specimens, low cell viability of processed peripheral blood mononuclear cells (PBMCs), or high assay background. Immunogenicity data from 17 phase 1 and 2 phase 2a HVTN vaccine trials, which began enrolling after June 2005 (data as of September 2014), indicate that 15% is a reasonable estimate for the rate of missing data at Month 6.5. For this reason, the sample size calculations below account for 15% enrolled participants having missing data for the primary immunogenicity endpoints.

10 STATISTICAL ANALYSIS

This section describes the final study analysis, unblinded as to treatment arm assignment. All data from enrolled participants will be analyzed regardless of how many vaccinations they received. Analyses are modified intent-to-treat in that individuals who are randomized but not enrolled do not contribute data and hence are excluded. Because of blinding and the brief length of time between randomization and enrollment—typically no more than 4 working days—very few such individuals are expected.

Analyses for primary endpoints will be performed using SAS and R. All other descriptive and inferential statistical analyses will be performed using SAS, StatXact, or R statistical software.

No formal multiple comparison adjustments will be employed for multiple safety endpoints, multiple primary immunogenicity endpoints, or secondary endpoints. However, multiplicity adjustments will be made for certain immunogenicity assays, as discussed below, when the assay endpoint is viewed as a collection of hypotheses (eg, testing multiple peptide pools to determine a positive response).

10.1 Safety/tolerability analysis

Since enrollment is concurrent with receiving the first vaccination, all participants will have received at least 1 vaccination and therefore will provide some safety data.

10.1.1 Reactogenicity

The number and percentage of participants experiencing each type of reactogenicity sign or symptom will be tabulated by severity and treatment arm and the percentages displayed graphically by arm. For a given sign or symptom, each participant's reactogenicity will be counted once under the maximum severity for all injection visits. In addition to the individual types of events, the maximum severity of local pain or tenderness, induration or erythema, and of systemic symptoms will be calculated. Kruskal-Wallis test will be used to test for differences in severity between arms.

10.1.2 AEs and SAEs

AEs will be summarized using Medical Dictionary for Regulatory Activities (MedDRA) System Organ Class and preferred terms. Tables will show by treatment arm the number and percentage of participants experiencing an AE within a System Organ Class or within preferred term category by severity or by relationship to study product. For the calculations in these tables, a participant with multiple AEs within a category will be counted once under the maximum severity or the strongest recorded causal relationship to study product. Formal statistical testing comparing arms is not planned since interpretation of the magnitude of differences must rely heavily upon clinical judgment.

A listing of SAEs reported to the DAIDS Regulatory Support Center (RSC) Safety Office will provide details of the events including severity, relationship to study product, time between onset and last vaccination, and number of vaccinations received.

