2.6 Rationale for Lymph Node Fine Needle Aspiration

A subset of participants (approximately 1/2 of each group at the 100 mcg dose level) will undergo fine-needle aspiration (FNA) of the axillary draining lymph node after each dose of BG505 MG39.3 mRNA vaccines to gain understanding on how the magnitude and kinetics of germinal center (GC) B and T-cell responses may differ between: a) soluble and membrane trimers and b) CD4KO and WT-CD4bs membrane trimers. The analysis of these FNA/GC responses will be compared to FNA/GC responses in NHPs administered the same immunogens, thus allowing for greater understanding of how and whether NHP responses can be used to predict human responses. The FNA/GC responses here will also provide baseline data on human GC responses to trimer mRNA immunization that can be evaluated relative to future adjuvanted protein trimer immunization studies. This same subset will have samples collected for B-cell sorting and sequencing to obtain information on the B cell receptor (BCR) repertoires of the GC and memory B cells induced by these mRNA immunogens, in particular to look for differences in BCR repertoire responses between: a) soluble and membrane trimers and b) CD4KO and WT-CD4bs membrane trimers.

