2.7 Rationale for Leukapheresis

This protocol will employ leukapheresis also in approximately 1/2 of each group at the 100 mcg dose level to ensure adequate specimens for analysis of rare precursors. Leukapheresis will be performed after the second and third doses of BG505 MG39.3 mRNA vaccines have been administered. The rationale for performing leukapheresis two weeks post vaccination is based upon detailed

preclinical investigations into the kinetics of the germinal center response in rhesus macaques (10).

Samples collected through leukapheresis after the second and third vaccine administration will be used for MHC Class II human leukocyte antigen (HLA) typing and CD4+ T-cell epitope mapping to understand the breadth and potency of CD4 epitopes in these trimers. These studies will a) provide insight into how soluble, membrane-bound, and membrane-bound-CD4KO trimers may differ in their induction of CD4+ T-cell responses and b) most importantly, assist design of future sequential immunization regimens that incorporate these trimers to ensure that T-helper epitopes that are cross-reactive over vaccine recipients and common MHC alleles are shared among different immunogens in the regimen.

To assess the expansion of antigen specific precursor B cell populations and CD4+ T-cell repertoire large numbers of peripheral blood mononuclear cells (PBMCs) are required. There are approximately 1 million PBMCs per milliliter of blood and therefore peripheral blood sampling at volumes associated with typical blood donation (~500 mL) would not provide sufficient PBMC numbers. Leukapheresis can provide 6-10 billion PBMCs without depleting red blood cells or other blood components.

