Rare risks with any injection procedure include infection at the site of injection. Signs of infection at the injection site include severe pain, erythema, induration, warmth or drainage. There are rare reports of anaphylaxis with many vaccines. There may be side effects from the study products which may be serious or life threatening that we do not know about yet.

If antibodies elicited by the study vaccine result in a positive or indeterminate HIV test (ie, vaccine-induced seropositivity or VISP), this may have a negative impact on employment, health care, insurance, travel, and personal relationships. HIV polymerase chain reaction (PCR) will be used to exclude or confirm HIV infection.

Blood drawing may cause pain, bruising, fainting, and, rarely, infection at the site where the blood is taken. Leukapheresis can also cause pain, bruising, and, rarely infection. Additional risks may depend on local leukapheresis procedures. Fainting can also occur, but occurs less frequently than with blood drawing.

Fine needle aspiration of lymph nodes can uncommonly cause pain, bruising, and/or bleeding at the site where the needle is inserted. Similar to any procedure where a needle is inserted into the skin (such as vaccination, as described above), there is a rare risk of localized infection. The local anesthetic rarely can cause temporary arm numbness or weakness.

Risks during Pregnancy: Because possible effects of the study vaccine on a fetus or nursing infant are unknown, persons assigned female sex at birth who have

reproductive potential will be tested for pregnancy at screening and prior to administration of each dose of study vaccine. Such persons will be asked to notify the site immediately if they suspect or learn they are pregnant during this study. In case of pregnancy, participants will continue to be followed for safety and the participant will not receive any additional vaccinations. The participant will be contacted about the outcome of a pregnancy that begins during the study.

Other Risks: The medical tests performed as part of this research protocol may result in new diagnoses or abnormal values without clinical significance.

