6.2 Randomization

Participants will first be randomized in a 1:1:1 ratio into the Part A sentinel safety cohort. If safety criteria are met, enrollment will proceed with Part B sentinel group of n=12 with 1:1:1 randomization and the remainder of Part A (n=42) with 1:1:1 randomization, with some sites enrolling into the Part B sentinel cohort while other sites are enrolling the remainder of Part A. Once the safety criteria for the Part B sentinel safety cohort have been met, the remaining Part B participants (n=42) will be enrolled with 1:1:1 randomization.

Randomization to Groups 1-3 will be stratified by willingness to consent to FNA and/or leukapheresis. A maximum of 27 participants in total that do NOT consent to either FNA and leukapheresis collection will be enrolled.

A participant's randomization assignment will be computer generated and provided to the HVTN CRS pharmacist through a web-based randomization system. At each institution, the pharmacist with primary responsibility for dispensing study products is charged with maintaining security of the treatment assignments (except in emergency situations as specified in the HVTN Manual of Operations [MOP]).

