8.5 Additional procedures for Part A participants

Approximately half of the participants in Part A (groups 1-3) will undergo lymph node FNA and half will have leukapheresis performed. These procedures require that participants meet additional eligibility criteria (see Sections 5.1.3, 8.5.1 and 8.5.2). The participants willing to undergo these procedures may choose to have only lymph node FNA, only leukapheresis, or both procedures. Other participants in Part A may choose to have neither procedure performed.

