11 SAFETY TABLES, PARTICIPANT LISTINGS, AND FIGURES

11.1 List of Tables

The following tables are included in the SMB reports and FSR for Safety:

- Enrollment Report
- Demographics and Vaccination Frequencies
- Overall Protocol Status
- Maximum Local and Systemic Reactogenicity Summaries
- Adverse Experiences by Body System and Severity – By Decreasing Frequency
- Adverse Experiences by Preferred Term and Severity – By Decreasing Frequency – Includes Severe, Life-threatening or Fatal Experiences Only
- Adverse Experiences by Preferred Term and Severity – By Decreasing Frequency – Includes Experiences of All Severities
- Adverse Experiences by Preferred Term and Relationship to Study Product – By Decreasing Frequency – Includes Related Experiences Only
- Adverse Experiences by Preferred Term and Relationship to Study Product – By Decreasing Frequency – Includes Experiences of Any Relationship
- Expedited Adverse Experiences (EAEs) Reported to the Regulatory Support Center (RSC)
- Pregnancy Listing

Additional tables included in the FSR for Safety:

- Social Impact Summary
- FNA/Leukapheresis Related Events
- Listing of Urticaria Adverse Events
- End of Study Diagnostic Testing Results for Vaccinees
- Local Lab Value Summary Statistics
- Local Laboratory Values Meeting Grade 1 AE Criteria or Above

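### The by-arm tables of all adverse events include FNA and leukapheresis events, which can arise only in the 100 mcg groups; matching severity tables without sample-collection events are needed to read dose differences

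*SAP*

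**What the plan says.** Protocol 8.5 confines the procedures to the lower dose: "Approximately half of the participants in Part A (groups 1-3) will undergo lymph node FNA and half will have leukapheresis performed". Protocol 5.1.3 gives the number as three FNAs and two leukaphereses. Protocol 6.2 adds a cap: "A maximum of 27 participants in total that do NOT consent to either FNA and leukapheresis collection will be enrolled".

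Primary endpoint 1 (Protocol 3.1, SAP 4) includes all AEs for 30 days after vaccination. SAP 10.1.2 tabulates them by arm, by severity or by relationship to product, counting each participant once per category at the worst grade or strongest relationship: "Tables will show by treatment arm the number and percentage of participants experiencing an AE within a System Organ Class". SAP 11.1 lists five such tables. Three are by severity and cover all causes; two are by relationship, one of them limited to related events. Nothing says whether events caused by a sampling procedure are left out or marked.

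SAP 6 names as the threat "confounding by adverse events not related to the vaccine that by chance occur more often in one arm of the trial than another", and answers it with the reported relationship to product. SAP 11.1 also lists a table called "FNA/Leukapheresis Related Events", but only among the additional tables for the Final Study Report (FSR).

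**The concern.** The imbalance here is not a matter of chance. One dose level undergoes two procedures that the other never has. Protocol 2.8.1 expects side effects from both: FNA can uncommonly cause pain, bruising or bleeding, and "Leukapheresis can also cause pain, bruising, and, rarely infection".

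Protocol 2.5 gives finding the maximum tolerable dose as a reason for testing two levels, and Protocol 2.3 expects the weekly unblinded reports to help safety monitoring across dosing groups. A reader of the severity tables who sees similar rates at 100 and 250 mcg cannot tell whether procedure events have contributed. Because each participant is counted once per category at the worst grade, procedure events cannot be subtracted from the printed counts. No listed table gives severity among product-related events alone, so the relationship tables do not fill the gap.

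**Working it through.** The documents give no event rate for either procedure, so there is no figure of the plan's own to reproduce. All rates below are assumptions.

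**Timing.** Days after vaccination = target day minus day of the preceding vaccination (Protocol Appendix D), set against the 30-day AE window (Protocol 9.1).

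- FNA 1: 43 − 1 = 42 days (allowable 35-49). Outside the window, although Appendix A still marks AE recording at Visit 5.
- Leukapheresis 1 and 2: 71 − 57 = 14 and 183 − 169 = 14 days (allowable 10-18). Inside.
- FNA 2 and 3: 85 − 57 = 28 and 197 − 169 = 28 days (target 24-32, allowable 21-35). Inside when on target, with two days of the window left; outside if done on days 31-35.

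**Share of an arm with a procedure, s.** About 9 of 18 have FNA and about 9 of 18 leukapheresis. If the same people have both, s = 0.5; if no one has both, s = 1.0. Reading the cap against Part A's 54, at least 54 − 27 = 27 (50%) have one or both.

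**Size, ignoring any counterpart at 250 mcg.** Let b be the proportion with a non-procedure event in a table row, and q the chance that a participant with a procedure has a procedure event in that row. Observed 100 mcg proportion = b + (1 − b) × s × q. With b = 10%, s = 0.5, a true 20% at 250 mcg and 54 per dose level:

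| q | Observed at 100 mcg | Rise (points) | Extra per 54 | Apparent excess at 250 mcg (points) | Chance that the 250 mcg count is higher |
|---|---|---|---|---|---|
| 0% | 10% | 0 | 0 | 10 | 0.91 |
| 5% | 12.25% | 2.25 | 1.2 | 7.75 | 0.84 |
| 10% | 14.5% | 4.5 | 2.4 | 5.5 | 0.74 |
| 20% | 19% | 9 | 4.9 | 1 | 0.50 |
| 30% | 23.5% | 13.5 | 7.3 | −3.5 | 0.29 |

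The last column comes from two independent exact binomials. Over b = 0-40% and q = 5-30%, the rise is 1.5 points (0.6 × 0.5 × 0.05) to 15 points (0.5 × 0.30) at s = 0.5, and 3 to 30 points at s = 1.0.

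**Offset for leukapheresis.** Participants without leukapheresis, including all of Part B, give PBMC draws of 144.5 mL at Visit 8 and 204 mL at Visit 12 instead (Appendix A footnote 14, Appendix B). Those with leukapheresis still give 180 − 144.5 = 35.5 mL and 229.5 − 204 = 25.5 mL at these visits. Protocol 2.8.1 lists pain, bruising and fainting for blood drawing, and says fainting is less frequent with leukapheresis.

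Let rL be the chance of an event from leukapheresis and rD the chance from the extra PBMC draw, in a row with no other events. With half of the 100 mcg arm having leukapheresis, 100 mcg minus 250 mcg = (0.5 rL + 0.5 rD) − rD = 0.5 × (rL − rD).

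- rL = 10%, rD = 0: +5 points.
- rL = 10%, rD = 5%: +2.5 points.
- rL = rD: 0.
- rL = 5%, rD = 10%: −2.5 points.

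If only FNA and leukapheresis events were taken out, 0.5 rD − rD = −0.5 rD would remain: 2.5 points against the 250 mcg arms at rD = 5%. FNA has no counterpart in Part B, so it has no such offset.

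**The case against.** The plan already separates part of this. SAP 6 brings in relationship to product, SAP 11.1 has a related-only table and the FSR procedure table, and SAP 11.2 gives the SMB listings of severe events and of events with relationship to product. An event judged unrelated to product drops out of the related-only table. This stands, but it leaves severity unaddressed, and the procedure table is not listed for the SMB reports.

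The main dose-safety decisions do not use these tables. Solicited reactogenicity covers seven days, before the earliest allowable leukapheresis (day 10) or in-window FNA (day 21). Sentinel reviews look at two weeks after the first dose, before any procedure. Pause rules depend on related SAEs, related grade 3-4 AEs, and myocarditis or pericarditis. No test of AEs between arms is planned, and the two dose levels are randomized separately (Protocol 9.6). All of this stands, and it limits the stakes to descriptive reading of the AE tables.

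A reader might go further and infer that AE rates at 100 mcg are inflated across the board, so that an increase at 250 mcg would be hidden. The documents do not support that. They give no procedure event rate and call FNA effects uncommon. Pain, bruising and bleeding at a needle site fall in a few recognizable terms and leave most rows untouched. In the table above, near-complete masking of a 10-point excess needs q of about 20%. The SAP lists no any-AE total in which all these events would add up. For fainting, the protocol's own statement points the other way.

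**Conclusion.** The point holds in a limited form. By design, the all-cause System Organ Class and preferred-term tables carry FNA and leukapheresis events in the 100 mcg arms only, and no stated rule separates them. SAP 6 does not recognize this source of imbalance. The effect lies mainly in procedure-type terms and the class rows containing them.

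The size cannot be fixed from the documents. The illustrations rest on assumed values of q and b, on s between 0.5 and 1.0, and, in the size table, on no offset from blood draws. For leukapheresis the net effect could be small or reversed in some rows; for FNA it can only raise the 100 mcg figures. It is an avoidable blur in a descriptive comparison, and does not show that the trial would miss a dose-related safety signal.

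**What to change.** In SAP 10.1.2 and 11.1, keep the all-AE tables. Add the same by-arm severity tables without AEs attributed to any sample-collection procedure (FNA, leukapheresis or blood draw), and state that dose-level differences in AE severity are read from these. Blood-draw events must be set aside too, because removing only FNA and leukapheresis events would tilt the contrast against 250 mcg.

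Put the FNA/leukapheresis event table in the SMB reports as well as the FSR, with participants who had the procedure as its denominator.

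The cost is SAP wording and reruns of existing table programs. The attribution already needed for the planned procedure table covers FNA and leukapheresis; blood-draw events need the same marking. The small downside is that the split rests on open-label attribution, which is why the all-AE tables stay. Setting Part A participants with neither procedure beside Part B can be shown, but only descriptively: that subgroup is self-selected, capped at 27 and has no minimum size.
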